## **Participants**

### Sample size estimation

A total of 154 participants will be enrolled at the three participating clinics. The following assumptions were used to derive this sample size:

Proportion of Placebo+MM/MC participants achieving >95% adherence = 20%

Proportion of Vivitrol+MM/MC participants achieving >95% adherence = 40%

Power=72%

Alpha level=0.05

Participants at the Nathan Smith Clinic will be 50 HIV-infected men and women who report heavy drinking, alcohol abuse or dependence. Referrals will come from within the Nathan Smith Clinic site, via local HIV care sites, website advertisements, local papers, community postings, community physicians, other patients, local mental health centers, local hospitals, and substance abuse treatment facilities.

***Inclusion criteria:*** Each subject must:

1. Be HIV-infected.
2. Currently be prescribed HAART medication.
3. Report less than 95% adherence to their HAART medication.
4. Report heavy drinking 4 or more times in the past 4 weeks, or meet current criteria for alcohol abuse or dependence. Heavy drinking is defined as 4 or more drinks for women and 5 or more drinks for men on one occasion.
5. Be at least 18 years old.
6. Be able to understand English and provide informed consent.

***Exclusion criteria:*** No subject may:

1. Be psychotic or severely psychiatrically disabled.
2. Be currently enrolled in formal treatment for alcohol (excluding self-help, e.g. Alcoholics Anonymous)
3. Have medical conditions that would preclude completing or be of harm during the course of the study.
4. Have laboratory or clinical evidence of significant liver dysfunction (alanine aminotransferase (ALT) or aspartate aminotransferase (AST) greater than 5 times the upper limit of the normal range) or cirrhosis with a Child-Pugh classification greater than A or B.
5. Have a known contraindication to NTX therapy (e.g. requiring opioid medication for pain).
6. Be pregnant, nursing or unable to use an effective method of birth control (women).
7. Patients with a positive urine opioid screen result
8. Known hypersensitivity to naltrexone, PLG (polylactide-co-glycolide, carboxymethylcellulose, or any other components of the diluent

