***Statistical analyses***

General considerations: Statistical procedures and models for analyzing data have been selected according to the research hypotheses being investigated and the types of data available. In general, p-values <0.05 will be considered statistically significant. When necessary, however, we will use appropriate corrections of p-values to account for multiple statistical tests. Statistical analyses will be conducted on an intention-to-treat sample using SAS Release 8.1 (SAS Institute, Inc., Cary, NC) and SPSS 14.0 (SPSS Inc., Chicago IL) statistical packages. Where appropriate, hypotheses will be tested by independent statistical analyses using Mixed Models procedure to test for significant effect of group assignment (VIVITROL vs. placebo), time, and the interaction between group assignment and time. Loss to follow-up is of concern in longitudinal analyses, particularly if loss to follow-up is differential. We plan to use established strategies (> 90% follow-up) to reduce loss to follow-up [122, 124]. A benefit of the mixed effects models approach is that subjects who do not have complete information on the outcome variable can be included, provided that missing data is missing at random.

**Specific Aim 1:** To compare the efficacy of VIVITROL +MM/MC versus placebo +MM/MC on adherence to HAART.

**Hypothesis 1:** VIVITROL +MM/MC will lead to improved adherence to HAART when compared to placebo + MM/MC.

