HAART medication adherence, specifically focusing on the proportion of patients achieving 95% or greater HAART adherence (See justification for this threshold in Section B.7.), will be evaluated using pharmacy fill/refill data on a monthly basis and self-report. For each month of the 24-week treatment period, and the 9 and 12 month follow-up periods, we will calculate the number of days of HAART medication adherence. Because HAART, the simultaneous use of  $\geq 3$  antiretroviral medications, is considered the standard of care for HIV-infected individuals, patients will be classified as adherent when their regimen medication possession ratio (MPR) (calculated as the days' supply of medication divided by the number of days between the first fill and the last refill [84]) is  $> 0.95$ , signifying greater than 95% adherence. We will also capture the MPR of all anti-retroviral medications. In prior work, we have shown that over a one year study period in VACS, the HAART MPR was 70% compared to 77% of any anti-retroviral total (Kim et al, unpublished). For patients who are on HAART but less than 95% adherent, we will determine what proportion of this group achieved greater than 95% adherence.

For primary outcome analysis, both aggregate and stratified analyses will be carried out to compare the proportion of participants in each of the two groups who achieve  $\geq 95\%$  adherence during the last four months of observation.

The probability of achieving the primary outcome will be modeled using logistic regression analysis. An unadjusted model (treatment) and models that include covariate adjustment (treatment plus other predictor variables eg depression, race, opiate receptor genetics, CD4 level, viral load level) will be executed.

In addition and, as appropriate, linear mixed effects models will be used to assess changes in adherence over the six months of observation. Models will include a fixed effect for treatment status, time as a continuous variable representing the month of observation, and the interaction between treatment and time in order to assess difference in slopes of change by treatment status. Random effects will be included to account for intra-subject correlation of repeated measures. Additional factors that may impact rate of change in adherence include time-varying covariates such as CD4 and viral load. Model fit will be assessed with analysis of residuals and other standard methods for assessing goodness-of-fit [136].

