### **Reporting to Alkermes**

Serious Adverse Events, regardless of attribution, shall be reported to Alkermes on FDA Form 3500 within 1 business day of discovery via fax or email:

Alkermes, Inc.

Attention: Alkermes Drug Safety

Dedicated Safety [contact]

Dedicated email: [[contact]](mailto:[contact])

The written report must include the opinion of the study site's PI or designated sub-investigator as to whether the event is related to the study drug. If this relationship is determined to be possibly, probably, or definitely related to study drug, evidence to support this assessment must be provided.

The PI is responsible for monitoring the data and conducting performance and safety reviews, at the specified frequency. Either the PI or the IRB have the authority to stop or modify the study. The monitoring by the IRB will occur annually at the time of re-approval. The PI will conduct data and safety review at least quarterly and at any time a serious adverse event occurs. During the review process, the PI will evaluate whether the study should continue unchanged, requires modification or amendment to continue, or should be closed to enrollment.

During the follow-up period, any patient requiring additional intervention due to significantly increased alcohol consumption or serious psychiatric/medical symptoms will receive a referral to treatment. In addition, any and all adverse events during the follow-up period will be reported to the IRB and the Project Officer at NIAAA with serious adverse events being reported within 48 hours.

We plan to comprise the Data Safety and Monitoring Board (DSMB) with experts in antiretroviral medications and addiction pharmacotherapies. The DSMB will review the progress of the study, and also conduct an interim analysis. The DSMB will monitor the occurrence and frequency of serious adverse events on a quarterly basis and review the results of the interim analysis. The interim analysis will be conducted six months after 40 subjects have been randomized to either of the treatment groups or when all of the 40 subjects in each group have completed the treatment protocol, whichever comes first. The interim analysis will evaluate whether the proportion of subjects achieving >95% adherence differs significantly (at  $p < .05$ ) by treatment condition. This interim analysis will determine whether one of the interventions is significantly inferior to the other on the primary outcome of improving HAART adherence.

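### The interim look tests the primary endpoint at an unadjusted p<.05 with no stated consequence; if either look can be acted on or claimed, two-sided type I error is about 5% to 8%, depending on the test

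*Combined protocol and SAP*

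**What the plan says.** The interim analysis is described at the end of Section IX.3, under the heading Reporting to Alkermes. The DSMB is to carry out the analysis and review it: "The interim analysis will evaluate whether the proportion of subjects achieving >95% adherence differs significantly" between arms, at p below .05. The stated purpose is "This interim analysis will determine whether one of the interventions is significantly inferior to the other on the primary outcome". It takes place either six months after 40 participants have been randomised (the text is unclear whether this is in total or per arm) or "when all of the 40 subjects in each group have completed the treatment protocol", whichever is earlier.

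The same section says "Either the PI or the IRB have the authority to stop or modify the study". It neither ties that authority to the interim result nor separates the two.

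Elsewhere the trial keeps the whole 5%. Sample size estimation (Section V.3) gives "Alpha level=0.05", and Statistical analyses (Section V.4) says "In general, p-values <0.05 will be considered statistically significant". Section V.4 adds "When necessary, however, we will use appropriate corrections of p-values to account for multiple statistical tests", without a method and without mentioning the interim. For the final analysis it says "The probability of achieving the primary outcome will be modeled using logistic regression analysis"; it does not say whether the Wald, score or likelihood-ratio test is used.

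**The concern.** The primary endpoint is tested twice, each time at the full 0.05, and nothing says what a significant first result leads to. The stated purpose is neutral as to direction. If placebo turned out to be the inferior arm, that would be an early conclusion of benefit.

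Three things are at stake.

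- If either look can be acted on or claimed, the trial is not held to the error rate of the single 0.05 test that its sample size assumes.
- A reader of the final p-value cannot tell what error rate it carries, because that depends on an action and a test that the plan does not state.
- An effect declared at an unadjusted mid-trial look overstates the true effect on average.

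**Working it through.** **Inputs.** 154 participants, 20% versus 40% achieving the adherence threshold, alpha 0.05 and power 72% (Sample size estimation); 1:1 allocation, so 77 per arm (Treatment section, 50% chance of active drug); interim at 40 per arm (Section IX.3). Assumptions: two-sided tests, outcome known for all 80 at the interim, information proportional to participants, no dropout.

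**1. Reproduce the stated power.** With n = 77 per arm and a mean rate of 0.30:

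- SE under the null = sqrt(2 × 0.3 × 0.7/77) = 0.0739
- SE under the alternative = sqrt((0.2 × 0.8 + 0.4 × 0.6)/77) = 0.0721
- Uncorrected: Φ[(0.20 − 1.96 × 0.0739)/0.0721] = 77.8%
- Continuity-corrected (subtract 1/77 = 0.0130 from the difference): 72.1%

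Of the versions tried, only the continuity-corrected one gives the stated 72%.

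**2. Two looks, normal theory.** The information fraction is 80/154 = 0.52, and the correlation of the two statistics is sqrt(0.52) = 0.72.

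- P(|Z1| > 1.96 or |Z2| > 1.96) = 8.2%.
- False-benefit rate (upper side only): 4.1% if either direction counts at the interim, against 2.5% for one look.
- False-benefit rate if only a result adverse to VIVITROL could stop the trial: 2.5%.

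**3. Two looks, exact.** All binomial outcomes were enumerated at 40 then 77 per arm, with 0.05 at both looks and equal true rates in the arms:

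| Test | Rate 20% | 25% | 30% | 35% | 40% | Single final look |
|---|---|---|---|---|---|---|
| Chi-square, continuity-corrected | 4.57% | 5.02% | 5.17% | 5.30% | 5.45% | 3.1% to 3.5% |
| Logistic Wald, unadjusted model | 7.19% | 7.72% | 7.86% | 8.22% | 8.45% | 4.5% to 5.1% |
| Chi-square, uncorrected | 8.44% | 8.29% | 8.12% | 8.31% | 8.63% | 5.0% to 5.3% |

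The logistic likelihood-ratio test gives 8.5% to 8.7% (rates of 20%, 30% and 40%), and Fisher's test 5.0% to 5.6%.

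**4. Sensitivity to timing.** If the first trigger means 40 in total, the fraction is 40/154 = 0.26 and normal theory gives 9.0%. Exact values at a 20% rate are 9.2% (uncorrected), 9.6% (likelihood ratio), 6.4% (Wald) and 4.6% (continuity-corrected).

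**5. How often the threshold is crossed.** Under the planned 20% versus 40%, with 40 per arm, the interim is significant with probability 0.497 (uncorrected), 0.495 (Wald) or 0.405 (corrected). The mean observed difference is then 28.0, 28.0 or 29.5 points, against a true 20. A significant single final test also overstates, at 22.7 (uncorrected) or 23.3 points (corrected). The part due to the early look is therefore about 5 to 6 points.

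**The case against.** The strongest reply is that the harm depends on something the plan does not say. The interim sits in a safety-monitoring section, no efficacy stop or early claim is named, and the stated aim is to find an inferior arm. If only an adverse result could stop the trial, false benefit stays at 2.5%; if nothing follows from the look, there is no inflation. All of that stands, and the size is conditional for that reason. But the purpose is worded for either arm, an explicit significance threshold is attached, and no sentence makes the look advisory or limits it to harm. The plan therefore sets two full-level tests of the primary endpoint; it does more than leave out a detail.

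Secondly, the test that reproduces the 72% power gives only 4.6% to 5.5% over two looks. That is a live reading. Even so, its error rate rises from 3.1% to 3.5% at one look, and control near 5% would come from the conservatism of that test and not from any rule in the plan. The logistic model named for the primary outcome gives about 7% to 9%, depending on the test.

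Thirdly, the general promise to correct p-values could be read to cover a repeated test. It names no method, does not mention the interim, and does not override the .05 written for that look.

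Finally, the timing is ambiguous, and 40 in total would raise the upper end. The second trigger's reference to 40 in each group favours the per-arm reading used as the base case.

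**Conclusion.** The concern holds and should be fixed. The interim threshold is an unadjusted .05 on the primary endpoint, with no matching final level and no stated consequence. If either look can be acted on or claimed, the two-sided type I error is 8.2% in normal theory. In exact calculation it runs from about 5% with a continuity-corrected test to between 7% and 9% with the logistic or uncorrected tests. This rests on 40 per arm at the interim, two-sided testing and complete outcomes; with 40 in total the normal-theory figure is 9.0%. There is no inflation if the look is non-decisional, and none in the false-benefit rate if only an adverse result can stop the trial. The plan specifies neither. The gap is practical as well: under the design's own rates the DSMB would hold a significant result 41% to 50% of the time, with no instruction on what to do with it.

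**What to change.** In the interim-analysis paragraph of Section IX.3, choose one of two courses.

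- **Decisional look.** Replace the .05 with a group-sequential boundary, state the matching final level in Section V.4, and name the test for both looks. Two examples at 80 of 154, each holding 5.0% overall in normal theory: Haybittle-Peto, interim p<0.001 and final p<0.0498; or Lan-DeMets O'Brien-Fleming-type spending of 0.025 per side, interim p<0.0037 (z = 2.899) and final p<0.0488 (z = 1.970). State what follows if the boundary is crossed, in which direction, and who decides.
- **Non-decisional look.** State that the interim supports no efficacy claim and no stopping, and remove the significance threshold.

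Either way, say whether 40 means per arm or in total. The Lan-DeMets levels depend on it: at 40 in total they become about 0.00002 and 0.04999. Haybittle-Peto is much less sensitive.

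The cost is protocol and SAP wording, with no extra participants. In normal theory, overall power with Lan-DeMets falls from 72.1% to 71.9% (continuity-corrected) or from 77.8% to 77.6% (uncorrected); with Haybittle-Peto the loss is under 0.1 point. Exact enumeration with Lan-DeMets gives 73.0% to 72.1% (corrected, mostly discreteness) and 78.2% to 78.3% (uncorrected).

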#### **4. Confidentiality & Security of Data:**

a. What protected health information about subjects will be collected and used for the research?

**Baseline Assessments:**

Prior to entrance into the study each patient will undergo a medical history, physical and laboratory assessments [Complete blood count (CBC), chemistry panel, and viral hepatitis serologies]. A urine pregnancy test will be performed on female subjects and must be negative prior to beginning the study medication and will be checked monthly. Demographic data to be collected include age, gender, marital status, highest level education completed, employment, substance use history, duration of HIV disease, and a detailed HAART medication history. Charts will be extracted to collect information including medical co-morbidities, prior CD4 lymphocyte cell counts and HIV RNA levels, HAART medication history, and historical genotypic information from prior HIV drug resistance testing

**Informed consent:**

Subjects will be recruited for participation and provided with a written consent form requiring their witnessed signature (see attached). Only subjects capable of giving informed consent will be admitted into the study. Informed consent will be obtained by trained and highly qualified research personnel.

**Confidentiality:**

The computerized data collection and monitoring system consists of a data base system that records clinical and research activities, completion of scheduled assessments, and delivers computerized versions of most of research instruments used in this study. Research assistants use this database to monitor and schedule patients and activities and to administer study assessments. Data entry of non-computerized assessments is accomplished by using specialized data entry software (such as, SPSS Data Entry or Microsoft Access Data base) facilitating efficient data entry and allowing elimination of out-of-range values and double entry of data for detection of key punch errors.

All reports generated from this study will not contain any identifying information about the participants. Research records will be coded only by a number, and will be stored in locked cabinets. Data are stored behind the Yale's firewall on password-protected computers.

- b. How will the research data be collected, recorded and stored?
- c. How will the digital data be stored?  CD  DVD  Flash Drive  Portable Hard Drive  Secured Server  Laptop Computer  Desktop Computer  Other
- d. What methods and procedures will be used to safeguard the confidentiality and security of the identifiable study data and the storage media indicated above during the subject participation in the study?

Once enrolled, subjects will be given a unique study number, to which only members of our research team will have access. Study data will be kept protected and treated as confidential at all times. Computerized subject data will be password protected. Data will only be reported in aggregate. Data will be deidentified prior to formal data analysis, making individual subject identification impossible. Moveable devices will be encrypted to protect identifiable information, following University policy

- e. What mechanisms are in place to ensure the proper use and continued protection of these data after the subject participation in the study has ceased?

Any identifiable information that is obtained in connection with this study will remain confidential and will be disclosed only with subject permission or as required by U.S. or State

law. Once enrolled, subjects will be given a unique study number, to which only members of our research team will have access. Study data will be kept protected and treated as confidential at all times. Computerized subject data will be password protected. Data will only be reported in aggregate. Data will be deidentified prior to formal data analysis, making individual subject identification impossible.

f. What will be done with the data when the research is completed? Are there plans to destroy the identifiable data? If yes, describe how, by whom and when identifiers will be destroyed. If no, describe how the data and/or identifiers will be secured.

Upon completion of the study, all computerized subject datasets will be de-identified and stored in a password-protected study computer, to which only the PI, investigators and study personnel will have access. All paper files with subject information will remain in locked files in the study office of the PI, until they are destroyed, after all analyses are complete.

g. Who will have access to the protected health information? (such as the research sponsor, the investigator, the research staff, all research monitors, FDA, QUACS, SSC, etc.)

During an audit or program evaluation, representatives from the Yale Human Investigation Committee and from the National Institutes of Health may have access to subject data, but will strictly follow rules of confidentiality.

h. Which external or internal individuals or agencies (such as the study sponsor, FDA, QUACS, SSC, etc.) will have access to the study data?

Representatives from the Yale Human Investigation Committee and from the National Institutes of Health may have access to subject data, but will strictly follow rules of confidentiality.

i. If appropriate, has a Certificate of Confidentiality been obtained?

A Certificate of Confidentiality from the National Institute on Alcohol Abuse and Alcoholism will be obtained to insure the confidentiality of all records and data and to better protect subjects.

j. Are there any mandatory reporting requirements? (Incidents of child abuse, elderly abuse, communicable diseases, etc.)

This protocol will include testing for hepatitis and therefore all positive test results will be reported to the State of CT Department of Public Health.

5. **Potential Benefits:** Identify any benefits that may be reasonably expected to result from the research, either to the subject(s) or to society at large. (Payment of subjects is not considered a benefit in this context of the risk benefit assessment.)

While there is no guaranteed benefit from participating in this study, participants in this study may benefit from active study medication and MM/MC which may lead to cessation or reduction in alcohol use and improvement in their HAART medication adherence, reduction in risk of viral mutations, improved HIV biological markers, and reduced HIV risk behaviors. In addition, participants will be compensated for their participation. They will also receive a comprehensive evaluation, close monitoring of their HIV disease, and possible referrals for

